3.2 Evaluation of Lerapolturev Shedding

As described in Section 1.2.1 and in the IB, lerapolturev has been subjected to extensive non-clinical and clinical viral shedding studies. Non-human primate studies in Cynomolgus macaques were unable to detect lerapolturev in saliva, stool or urine up to 56 days post intracerebral inoculation, with a lerapolturev dose of $5 \times 10^9 \text{ TCID}_{50}^{28}$. Likewise, lerapolturev shedding was undetected in the stool (the main excretory pathway for polio) of participants treated with lerapolturev for rGBM following administration of intracerebral doses of up to $1 \times 10^{10} \text{ TCID}_{50}$ or in melanoma participants receiving 3 telerapolturev injections ($1 \times 10^8 \text{ TCID}_{50}$ each). These results combined with the requirement that all participants must receive a CDC-recommended immunizing vaccination against PV, as well as a PV booster prior to study entry (which has resulted in extremely high levels of neutralizing anti-PV antibodies in patients tested to date) the risk of extra-tumoral lerapolturev dissemination and shedding is predicted to be extremely low.

However, because lerapolturev shedding in melanoma participants receiving repeat injections of lerapolturev at the dose levels allowed in this study has not been fully characterized, the Sponsor will test for the presence of lerapolturev in stool and on the surface of lerapolturev-injected lesions (as well as on the internal and external surfaces of any occlusive dressings applied post-lerapolturev injection) for up to 25 participants who received lerapolturev injections using the **Q3/4W** dosing schedule. For those participants enrolled using **QW** schedule of lerapolturev injections, viral shedding studies will be done in up to 25 participants as described in the appropriate SOA (Table 1 or Table 2 [Arm 2: lerapolturev + nivolumab]).

All samples related to the analysis of viral shedding may be collected during clinic visits, where feasible. Otherwise, samples may be collected at home and brought to the next clinic visit, as appropriate. Refer to the laboratory manual for additional details related to sample collection and storage.

3.3 Justification for Lerapolturev Dose and Schedule

The initial dose of lerapolturev evaluated in this trial was selected based on IND-directed toxicity studies and experience from ongoing studies in participants with rGBM or anti-PD-1 refractory melanoma (Section 1.2.2). Dose-range finding and toxicology studies in non-human primates documented the absence of viral encephalomyelitis, poliomyelitis and meningitis with intracerebral injection of lerapolturev up to a dose of 5 x 10^9 TCID₅₀³⁹.

Confidential Page 55 of 109

In the adult Phase 1 rGBM study, 4 participants were dosed at the maximum intended dose of 10^{10} TCID₅₀, injected intracerebrally, without signs of viral encephalomyelitis, poliomyelitis, or meningitis. However, due to persistent peri-tumoral inflammation and the continuing requirement for steroids in all participants, the recommended intracerebral dose was eventually reduced to 5×10^7 TCID₅₀.

In subcutaneous melanoma, the effect of inflammation is not expected to be as significant because cutaneous swelling is more easily managed than edema within the confines of the brain/skull. Data from the Phase 1 trial in anti-PD-1 refractory melanoma, as well as the currently available data generated during this study, has shown that a lerapolturev dose of up to 6 x 10⁸ TCID₅₀ is very well tolerated when given alone or in combination with anti-PD-1 therapy. All treatment-related AEs remain Grade 1 or 2, with no treatment-related SAEs, DLTs or evidence of CRS or ICANS in participants treated at any dose level (Section 1.2.2.2).

Therefore, this study has been amended to explore an approximately 2-fold higher lerapolturev dose using a dosing schedule (**QW**) with more frequent injections during the first 2 months of treatment followed by transition to a less frequent "maintenance" schedule. The rationale and data supporting this change are summarized in Section 1.3.

3.4 End of Study Definition

The study is considered completed with the last study assessment for the last participant participating in the study. The final data from the site will be sent to the Sponsor after completion of the final participant assessment at that study site, in the time frame specified in the clinical trial agreement.

4 STUDY POPULATION

The inclusion and exclusion criteria for enrolling participants in this study are described below. If there is a question about these criteria, the investigator must consult with the Sponsor or designee to resolve any issues prior to enrollment.

Screening for eligible participants will be completed within 28 days prior to Day 1. Refer to Section 4.3 for conditions under which repeat screening procedures are permitted.

4.1 Inclusion Criteria

- 1. ≥ 18 years of age
- 2. Prior CDC-recommended vaccination series against poliovirus (PV), and has received a boost immunization with trivalent IPOL® (Sanofi-Pasteur SA) at least 1 week, but less than 6 weeks, prior to Day 1
 - a. NOTE: Patients who are unsure of their vaccination status must provide evidence of anti-PV immunity prior to enrollment, as applicable

Confidential Page 56 of 109

- 3. Has biopsy proven unresectable cutaneous melanoma and is willing to undergo tumor biopsy prior to the first dose of study drug(s) and at prespecified intervals during the study. Note the following details:
 - a. Patients with ocular, acral or mucosal melanoma are not eligible
 - b. Patients with M1c or M1d disease are NOT eligible
 - c. Submission of an archival biopsy sample is allowed in lieu of the baseline tumor biopsy, provided the tissue is ≤4 months old and the participant received no intervening systemic/intratumoral anti-cancer therapy since the biopsy was acquired.
 - d. Must have at least 1 lesion that is amenable to biopsy. The lesion must be safely accessible as determined by the investigator and should not be located at sites that require significant risk procedures to biopsy. Examples of sites considered to be of significant risk include but are not limited to the following: the brain, lung, mediastinum, pancreas, or endoscopic procedures extending beyond the esophagus, stomach, or bowel wall.
- 4. Has ≥ 2 melanoma lesions that are accurately measurable by caliper or a radiological method according to RECIST 1.1 criteria
 - a. One lesion must be injectable--defined as a visible or palpable cutaneous, subcutaneous, or nodal melanoma lesion ≥ 10mm in longest diameter or multiple injectable melanoma lesions which in aggregate have a longest diameter of ≥ 10mm and where the minimal lesion size is ≥ 5mm.
 - b. Note that visceral lesions (eg, liver, lung, retroperitoneal, subpleural lesions) are not considered injectable for the purposes of this trial.
- 5. Has had confirmed progression of disease (PD) while receiving at least 6 weeks (> 1 dose) of an FDA-approved anti-PD-1/L1 therapy (as monotherapy or in combination) for the treatment of melanoma. Note the following details:
 - a. Initial PD as defined by RECIST v1.1
 - b. Confirmation of PD per iRECIST must occur by repeat assessment ≥ 4 weeks from initial evidence of PD, in the absence of rapid clinical progression.
 - c. Those who discontinue anti-PD-1/L1 therapy after at least 6 weeks (> 1 dose) and have confirmed PD per iRECIST within 12 weeks of their last anti-PD-1/L1 dose are also eligible, provided the anti-PD-1/L1 was not stopped due to toxicity requiring permanent discontinuation
 - d. Those treated with anti-PD-1/L1 in the adjuvant setting and who have biopsy-confirmed progression either while receiving anti-PD-1/L1-based therapy or ≤ 12 weeks after their last dose of anti-PD-1/L1 therapy are allowed

Confidential Page 57 of 109

NOTE: Adjuvant is defined as therapy received after surgical resection of disease such that the patient has no evidence of disease when the anti-PD-1/L1 therapy is initiated. Patients with known BRAF mutation must have also failed or refused to receive BRAF-targeted therapy (alone or in combination with MEK inhibitor) to be eligible

- 6. Eastern Cooperative Oncology Group (ECOG) status of 0-1
- 7. Serum lactate dehydrogenase (LDH) levels ≤3 x upper limit of normal (ULN)
- 8. Adequate bone marrow, liver and renal function as assessed by the following:
 - a. Hemoglobin ≥9.0 g/dl, patients may be transfused
 - b. Lymphocyte count ≥0.5 x 10⁹/L (500 μL)
 - c. Absolute neutrophil count (ANC) ≥1.5 x 10⁹/L (1500 µL)
 - d. Platelet count ≥100 x 10⁹/L (100,000 µL) without transfusion
 - e. AST, ALT, and alkaline phosphatase (ALP) ≤2.5 x upper limit of normal (ULN), with the following exceptions:
 - i. Patients with documented liver metastases: AST and ALT ≤5 x ULN
 - ii. Patients with documented liver or bone metastases: ALP ≤5 x ULN
 - f. Serum bilirubin ≤1.5 x ULN with the following exception:
 - i. Patients with known Gilbert disease: serum bilirubin level ≤3 x ULN
 - g. Measured or calculated (per institutional standards) creatinine clearance ≥30 ml/min (GFR can also be used in place of creatinine clearance)
 - h. For patients not receiving therapeutic anticoagulation: INR, PT, PTT (or aPTT) ≤1.5 x ULN
- 9. Life expectancy of >12 weeks
- 10. Signed informed consent form (ICF) indicating that participant understands the purpose of, and procedures required for the study, and is willing/able to participate in the study

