 - a. One lesion must be injectable--defined as a visible or palpable cutaneous, subcutaneous, or nodal melanoma lesion ≥ 10mm in longest diameter or multiple injectable melanoma lesions which in aggregate have a longest diameter of ≥ 10mm and where the minimal lesion size is ≥ 5mm.
 - b. Note that visceral lesions (eg, liver, lung, retroperitoneal, subpleural lesions) are not considered injectable for the purposes of this trial.
- 5. Has had confirmed progression of disease (PD) while receiving at least 6 weeks (> 1 dose) of an FDA-approved anti-PD-1/L1 therapy (as monotherapy or in combination) for the treatment of melanoma. Note the following details:
 - a. Initial PD as defined by RECIST v1.1
 - b. Confirmation of PD per iRECIST must occur by repeat assessment ≥ 4 weeks from initial evidence of PD, in the absence of rapid clinical progression.

Confidential Page 12 of 109

- c. Those who discontinue anti-PD-1/L1 therapy after at least 6 weeks (> 1 dose) and have confirmed PD per iRECIST within 12 weeks of their last anti-PD-1/L1 dose are also eligible, provided the anti-PD-1/L1 was not stopped due to toxicity requiring permanent discontinuation
- a. Those treated with anti-PD-1/L1 in the adjuvant setting and who have biopsy-confirmed progression either while receiving anti-PD-1/L1-based therapy or ≤ 12 weeks after their last dose of anti-PD-1/L1 therapy are allowed

NOTE: Adjuvant is defined as therapy received after surgical resection of disease such that the patient has no evidence of disease when the anti-PD-1/L1 therapy is initiated. Patients with known BRAF mutation must have also failed or refused to receive BRAF-targeted therapy (alone or in combination with MEK inhibitor) to be eligible.

- 6. Eastern Cooperative Oncology Group (ECOG) status of 0-1
- 7. Serum lactate dehydrogenase (LDH) levels ≤3 x upper limit of normal (ULN)
- 8. Adequate bone marrow, liver and renal function as assessed by the following:
 - a. Hemoglobin ≥9.0 g/dl, patients may be transfused
 - b. Lymphocyte count ≥0.5 x 10⁹/L (500 µL)
 - c. Absolute neutrophil count (ANC) ≥1.5 x 10⁹/L (1500 µL)
 - d. Platelet count ≥100 x 10⁹/L (100,000 µL) without transfusion
 - e. AST, ALT, and alkaline phosphatase (ALP) ≤2.5 x upper limit of normal (ULN), with the following exceptions:
 - i. Patients with documented liver metastases: AST and ALT ≤5 x ULN
 - ii. Patients with documented liver or bone metastases: ALP ≤5 x ULN

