4.2 Exclusion Criteria

- 1. Has biopsy-proven ocular, acral or mucosal melanoma
- 2. Has M1c or M1d disease
- 3. No more than one prior systemic anti-cancer regimen (monotherapy or combination) for management of melanoma. Additional details noted below:
 - a. Adjuvant anti-cancer therapy administered ≥ 6 months prior to the first injection of lerapolturev does NOT count as a line of treatment.
 - b. Patients with BRAF mutant melanoma may enroll if they have received ≤ 2 prior lines of systemic anti-cancer therapy only if one of those lines of therapy was a BRAF-targeted regimen (alone or in combination with MEK inhibitor).
 - c. A line of therapy is defined as a regimen in which at least 2 doses of systemic anti-cancer therapy (monotherapy or combination) was administered, and the regimen was discontinued because of progressive disease.

Confidential Page 58 of 109

- 4. Uncontrolled tumor-related pain. Participants requiring pain medication must be on a stable regimen at study entry
 - a. Symptomatic lesions amenable to palliative radiotherapy (eg, bone metastases or metastases causing nerve impingement) should be treated prior to enrollment. Patients should be recovered from the effects of radiation. There is no required minimum recovery period
 - b. Asymptomatic metastatic lesions that would likely cause functional deficits or intractable pain with further growth (eg, epidural metastasis that are not currently associated with spinal cord compression) should be considered for loco-regional therapy if appropriate prior to enrollment
- 5. Grade ≥2 pleural effusion, pericardial effusion, or ascites
- 6. Active or history of autoimmune disease or immune deficiency within previous 2 years, with the following exceptions:
 - a. History of autoimmune-related endocrinopathy (e.g. adrenal insufficiency, hypothyroidism, Type 1 diabetes mellitus, etc.) that is managed by hormone replacement therapy (e.g. hydrocortisone, thyroid hormone, insulin, etc.)
 - b. Eczema, psoriasis, or lichen simplex chronicus with dermatologic manifestations only (eg, patients with psoriatic arthritis are excluded), provided all of the following conditions are met:
 - i. Rash must cover <10% of body surface area
 - ii. Disease is well-controlled at baseline and requires only low-potency topical corticosteroids

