 - iii. No occurrence of acute exacerbations of the underlying condition requiring psoralen plus ultraviolet A radiation, methotrexate, retinoids, biologic agents, oral calcineurin inhibitors, or high potency or oral corticosteroids within 12 months of Day 1
- 7. History of idiopathic pulmonary fibrosis, organizing pneumonia (eg, bronchiolitis obliterans), drug-induced or idiopathic pneumonitis, or evidence of active pneumonitis on screening chest computed tomography (CT) scan
 - a. History of radiation pneumonitis in the radiation field (fibrosis) is allowed
- 8. History of a positive HIV RNA test (HIV 1 or 2 RNA by PCR)
- 9. Known active hepatitis B virus (HBV) infection (chronic or acute)
 - NOTE: Participants with a negative HBsAg test and a positive total hepatitis
 B core antibody (HBcAb) test are allowed
- 10. Known active hepatitis C virus (HCV) infection
 - NOTE: History of a positive HCV antibody test, but negative HCV RNA test, is allowed
- 11. Active tuberculosis

Confidential Page 59 of 109

- 12. Significant cardiovascular disease, such as New York Heart Association Class II or greater cardiac disease, myocardial infarction, or cerebrovascular accident within 3 months of Day 1, unstable arrhythmia, or unstable angina
- 13. Has received prior systemic anti-cancer therapy including investigational agents within 4 weeks or 5 elimination half-lives—whichever is shorter—prior to treatment or has not recovered from all AEs due to previous therapies to ≤Grade 1 or baseline. Participants with ≤Grade 2 neuropathy are eligible
 - a. Note: Anti-PD-1/L1 within 4 weeks prior to Day 1 is allowed
 - If participant received major surgery, they must have recovered adequately from the toxicity and/or complications from the intervention prior to starting study treatment
- 14. History of other malignancy within 2 years prior to Day 1, with the exception of those with a negligible risk of metastasis or death (eg, resected cutaneous basal cell carcinoma, or other cancers with 5-year OS of >90%)
- 15. Severe infection within 4 weeks prior to Day 1, including, but not limited to, hospitalization for complications of infection, bacteremia, or severe pneumonia
 - a. Prophylactic antibiotics (eg, to prevent a urinary tract infection or chronic obstructive pulmonary disease exacerbation) are allowed
- 16. Prior allogeneic stem cell or solid organ transplantation
- 17. Treatment with a live, attenuated vaccine within 4 weeks prior to Day 1

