- 18. Treatment with systemic immunosuppressive medication within 4 weeks prior to Day 1, with the following exceptions:
 - a. Participants who received acute, low-dose systemic immunosuppressant medication or a one-time pulse dose of systemic immunosuppressant medication (eg, 48 hours of corticosteroids for a contrast allergy) are eligible
 - Patients receiving mineralocorticoids (eg, fludrocortisone), or systemic prednisone equivalent corticosteroid doses of <10mg per day are eligible for the study
- 19. Known hypersensitivity to pembrolizumab, nivolumab, or any of the respective excipients
- 20. Requires therapeutic anticoagulation and cannot discontinue anticoagulation safely during the day prior, day of, and day after each lerapolturev injection
 - a. NOTE: Participants receiving anticoagulation with warfarin at the time of study entry are allowed if they can be transitioned to an alternative anticoagulant (eg, low molecular weight heparin or direct oral anticoagulants) prior to the first dose of lerapolturev. Anyone transitioned from warfarin to an oral anticoagulant prior to the first dose of lerapolturev should have an INR <1.5x upper limit of normal in order to participate. Antiplatelet agents (eg, aspirin, clopidogrel, etc.) are not considered anticoagulants for the purposes of this study (ie, are allowed)

Confidential Page 60 of 109

- 21. A pregnant or nursing female, or women of child-bearing potential and men who are sexually active and not willing/able to use medically acceptable forms of contraception starting from signed ICF through 150 days after last anti-PD-1 dose
- 22. History of human serum albumin allergy
- 23. History of neurological complications due to polio virus infection
- 24. History of agammaglobulinemia
- 25. Concurrent participation in a separate interventional clinical trial during this study
- 26. Any underlying medical condition for which, in the opinion of the investigator, participation would not be in the best interest of the participant (eg, compromises the participant's well-being) or that could prevent, limit, or confound protocol-specified assessments

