 Any adverse event affecting an organ system through an autoimmune or inflammatory mechanism, whereby the immune system is acting against normal tissue. Examples of irAEs, as well as recommendations for study drug management in the event of an irAE are described in Section 5.5.

Definition of Adverse Events of Interest (AESI):

An AESI is defined as:

Any AE (serious or non-serious) of scientific and medical concern for which
ongoing monitoring and communication by the investigator to the Sponsor or
designee may be appropriate. Such events may require further investigation to
characterize and understand them. Any AESI should be entered in the eCRF.

Confidential Page 92 of 109

Because lerapolturev is an immunotherapeutic administered by intratumoral injection, AESIs fall into 2 categories: 1.) AEs related to lerapolturev administration (ie, ISR), and 2.) AEs related to CRS and ICANS, which can occur when the body's immune cells release a bolus of inflammatory cytokines in response to an immunotherapeutic⁴⁴. AESI related to CRS and ICANS should be reported to the Sponsor within 24 hours, regardless of severity or seriousness. AESI related to ISR does not require expedited reporting (ie, within 24 hours), unless considered an SAE. A brief overview of each AESI is outlined below.

AEs associated with ISR:

To more completely describe the signs and symptoms associated with ISR, additional information related to the parameters outline below should be collected, which have been adapted from FDA guidance for evaluating ISR in vaccine trials⁴⁵ (see Appendix I), as well as past clinical experience with lerapolturev in melanoma.

- Erythema
- Induration
- Pruritus
- Ecchymosis/bruising/skin discoloration
- Pain

Each symptom will be graded on a scale of 1 to 4, as described in Appendix I, which may represent a measure of intensity, *not seriousness*. Thus, a Grade 3 or Grade 4 sign or symptom may be severe, but not necessarily serious. Therefore, although all Grade 3/4 AEs of ISR should be reported within 24 hours, only AEs of ISR meeting the criteria for seriousness (see SAE definition above for a definition of seriousness) should be reported as an SAE. Where appropriate, reporting of symptoms may also require a measurement recorded as a continuous variable (ie, diameter of erythema).

AEs associated with CRS and ICANS:

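### Criterion 5d omits the 5c proviso on anti-PD-1/L1 stopped for toxicity, leaving a narrow gap for fully resolved, non-pulmonary toxicity in adjuvant patients

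*Protocol*

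**What the plan says.** Inclusion criterion 5 in Protocol Section 4.1 defines failure of earlier anti-PD-1/L1 therapy. Two of its sub-items admit patients whose progression came after the drug was stopped.

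- **5c** covers patients who stopped after at least 6 weeks of treatment and had iRECIST-confirmed progression within 12 weeks of the last dose, "provided the anti-PD-1/L1 was not stopped due to toxicity requiring permanent discontinuation".
- **5d** has two branches. The first covers "Those treated with anti-PD-1/L1 in the adjuvant setting and who have biopsy-confirmed progression either while receiving anti-PD-1/L1-based therapy". The second, the after-last-dose branch, says that adjuvant patients who progress "≤ 12 weeks after their last dose of anti-PD-1/L1 therapy are allowed".

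The synopsis repeats both sub-items and again attaches the proviso to 5c only.

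The trial then gives anti-PD-1 again. Arm 2 starts it at Cycle 1 Day 1 (Tables 1 and 2). Participants on monotherapy may cross over to it (Section 3.1.1), and the three crossover criteria concern response and time on study, not earlier toxicity. Section 5.3 prefers the drug that the patient previously failed. It ties dosing to the package insert, including delay or discontinuation for immune-related adverse events (irAEs).

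**The concern.** A patient whose anti-PD-1/L1 was permanently stopped for toxicity, and who progressed within 12 weeks, is barred by 5c. If the drug had been given as adjuvant therapy, 5d taken as written admits a patient with the same history in the same window. No exclusion or crossover criterion states the missing bar. Such a patient could be given the same class of drug again, and where possible the same drug. What is at stake is the safety of a few patients, not the efficacy inference.

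**Working it through.** No arithmetic in the plan bears on this point, so the check compares texts.

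**Step 1. The two routes side by side (Section 4.1).**

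| | 5c | 5d, after-last-dose branch |
|---|---|---|
| Window after last dose | 12 weeks | 12 weeks |
| Proof of progression | iRECIST confirmation | Biopsy |
| Proviso on stopping for toxicity | Yes | None |

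One of the two routes carries the proviso. The other branch of 5d, progression during treatment, is not affected, because the drug had not been stopped when the disease progressed.

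**Step 2. What the other criteria catch.** 5c does not define the toxicity it refers to. The nearest list is the permanent-discontinuation list in Section 5.5.2, which governs management on treatment and is not an eligibility screen.

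- *Unresolved toxicity.* Exclusion 13 bars a patient who "has not recovered from all AEs due to previous therapies to ≤Grade 1 or baseline". Exclusion 18 bars "Treatment with systemic immunosuppressive medication within 4 weeks prior to Day 1", so a patient still on 10 mg/day or more of prednisone equivalent generally fails. AST or ALT above 2.5 x ULN, or bilirubin above 1.5 x ULN, fails inclusion 8e or 8f outside the stated exceptions.
- *Pneumonitis, resolved or not.* Exclusion 7 bars a history of "drug-induced or idiopathic pneumonitis". It names drug-induced toxicity for the lung only.
- *Hypersensitivity.* Exclusion 19 covers pembrolizumab and nivolumab. A Grade 3 or 4 infusion reaction plausibly falls here.
- *Resolved immune toxicity elsewhere.* Exclusion 6 bars "Active or history of autoimmune disease or immune deficiency within previous 2 years". Section 9.2 defines an irAE as "Any adverse event affecting an organ system through an autoimmune or inflammatory mechanism, whereby the immune system is acting against normal tissue". Exception 6a spares endocrinopathy managed with hormone replacement, which parallels a carve-out in Section 5.5.2. Read together, these suggest that exclusion 6 can reach a resolved immune colitis or hepatitis. It does not name irAEs, so sites may differ.
- *Anything else.* Exclusion 26 leaves it to the investigator's judgement.

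What is left is fully resolved toxicity outside the lung, in adjuvant patients on the after-last-dose branch, where a site reads exclusion 6 narrowly and does not use exclusion 26.

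**Step 3. A worked case (hypothetical).** An adjuvant patient has Grade 4 colitis, for which Section 5.5.2 requires permanent discontinuation. The colitis recovers to Grade 1 or better, and steroids end more than 4 weeks before Day 1. A biopsy confirms progression 10 weeks after the last dose. Since 10 ≤ 12, 5d is met. Exclusions 7, 13, 18 and 19 do not apply. Entry then turns on exclusions 6 and 26. Under 5c the same history is barred outright.

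**Step 4. Exposure.** With 1:1 randomisation, 1/(1+1) = one half of any such randomised patients would be expected to be assigned anti-PD-1 from Day 1, and crossover can add more. How many enter cannot be derived, because the documents give neither the share of adjuvant patients nor the rate of stopping for toxicity.

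**The case against.** There are four fair arguments on the other side.

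1. *5c may already govern.* It is not worded as excluding adjuvant patients, and 5a to 5d are all details of one criterion. A site could read 5d as changing only how progression is shown. That reading is possible but not explicit: 5d has its own standard of proof and ends by admitting the patient. Section 4 requires sponsor consultation when a question arises, but 5d as worded need not raise one.
2. *Exclusion 6 covers the main residual cases.* This stands in part, and it is why the gap is small. However, the same exclusions apply to 5c patients, and the proviso was still written for them.
3. *Section 5.3 ties dosing to the package insert, including discontinuation for irAEs, and crossover is optional.* A site may therefore withhold the drug. This governs dosing rather than eligibility. The insert is not among the documents, so how far it closes the gap cannot be settled.
4. *The proviso may serve the definition of resistance.* The Amendment 4 summary describes the change to criterion 5 in those terms. A reader might infer that the sponsor judged this toxicity history unsafe for re-treatment, but the documents give no such reason. The point rests on what the wording permits, not on a presumed motive.

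**Conclusion.** The inconsistency is real and its reach is narrow. It is a minor point of patient safety. The number affected is unknown and may be zero. No sample size, confidence interval or power figure changes.

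Two stronger readings are tempting, and the documents support neither. A reader might infer that 5d opens the trial to anyone with serious earlier immune toxicity. Inclusion 8e/8f and exclusions 7, 13, 18 and 19 rule out much of that, and exclusion 6 may rule out more. A reader might also count ten permanent-discontinuation events in Section 5.5.2, note that only pneumonitis is named as a resolved history, and conclude that the other nine go unscreened. That count ignores the criteria that catch those events while they are unresolved, and the infusion reactions that exclusion 19 plausibly covers.

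The conclusion assumes that 5d is read as a route of its own and that exclusion 6 is not applied uniformly to resolved irAEs. If the sponsor has instructed sites otherwise, the gap is already closed in practice.

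**What to change.** Add the 5c proviso to the after-last-dose branch of 5d, or make it an exclusion criterion, in both Section 4.1 and the synopsis. The cost is one clause in an amendment, and a few adjuvant-route patients become ineligible.

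For participants already enrolled, show the reason the earlier anti-PD-1/L1 was stopped in Listing 16.2.4.5.1 (SAP Sections 5.4 and 11), provided it is already captured. The documents do not show that it is, so this is cheap only if the data exist.

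The SAP is dated 19 November 2024, and the documents do not show whether enrolment is still open. If it has closed, the eligibility change protects nobody further and only the listing remains useful.
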